1.1.4 Sample Size Justification

This is an exploratory study, therefore the samples size is not based on statistical considerations. The aim for this study is to enroll 200 subjects. The assays to determine $A\beta$ from CSF are well established methods and the sample size justification for this current study is therefore based on previous research on amyloid pathology in CSF. In this study we select elderly at the age of 65 and higher of which at least a hundred will be above the age of 70. According to Jansen et al., (2015) we can expect at least 19% amyloid pathology in a 65+ population and 23% amyloid pathology among cognitively healthy 70+ elderly subjects. As we expect more responsiveness for study participation from elderly between the age of 65 till 70, based on our experience with previous studies in this age range, at least 100 subjects of >70 years old will be included in this study to be able to differentiate between age, which results in approximately 23 A β positive subjects versus approximately 77 A β negative subjects in this elderly age group. Along with approximately 19 A β positive subjects versus approximately 81 A β negative subjects in the age group 65-70 we expect to find at least 42 A β positive healthy elderly subjects. Based on previous comparable studies, these numbers are considered appropriate for a correlational study aimed at defining an algorithm [22, 23].

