1.1.9 Statistical methodology

Descriptive statistics will be used to summarize the data. Data will be graphically processed for visual inspection.

In order to develop an algorithm that can classify the subjects between ADpath+ and ADpath- there will be a two-step procedure. In the first step 500 bootstrap samples will be generated out of the original data and logistic regression with LASSO penalization (in order to account for the expected small event per variable ratio) in each of the bootstrap samples with all the candidate variables (CNS and biochemical outcome variables, age and educational level) will be performed. Out of all the candidate variables the ones that consistently and most frequently appear in the bootstrap models will be selected. Hence, in this first step the variable selection will take place. In the second step another 500 bootstrap samples will be generated and logistic regression will be performed (with penalization if necessary) in each of the bootstrap samples. This time only the variables that were selected in step 1 will be entered in the model. The estimates out of all the bootstrap models will be averaged and used in order to obtain predictions in the original data. Step two will result in the bootstrap-corrected predictions that will be assessed in terms of calibration (calibration slope), discrimination (c-index) and squared mean prediction error.

To investigate the relationship between biomarkers and gene carriers and NeuroCart scores, correlations and regression analyses will be used.

NeuroCart scores will be analysed with an analysis of variance (ANOVA) and/or multivariate analysis of variance (MANCOVA) to estimate differences between the groups of elderly with different $A\beta$ status.

The intra- and inter-individual diurnal fluctuation will be investigated with mixed-model analysis.

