9.8 CNS and biochemical endpoints

9.8.1 NeuroCart

All parameters will be listed by subject.

Parameters will initially be analysed without transformation, but if the data suggest otherwise, log-transformation may be applied.

Descriptive statistics will be used to summarize the data. Data will be graphically processed for visual inspection.

In order to develop an algorithm that can classify the subjects between ADpath+ and ADpath- there will be a two-step procedure. In the first step 500 bootstrap samples will be generated out of the original data and logistic regression with LASSO penalization (in order to account for the expected small event per variable ratio) in each of the bootstrap samples with all the candidate variables (CNS and biochemical outcome variables, age and educational level) will be performed. Out of all the candidate variables the ones that consistently and most frequently appear in the bootstrap models will be selected. Hence, in this first step the variable selection will take place. In the second step another 500 bootstrap samples will be generated and logistic regression will be performed (with penalization if necessary) in each of the bootstrap samples. This time only the variables that were selected in step 1 will be entered in the model. The estimates out of all the bootstrap models will be averaged and used in order to obtain predictions in the original data. Step two will result in the bootstrap-corrected predictions that will be assessed in terms of calibration (calibration slope), discrimination (c-index) and squared mean prediction error.

To investigate the relationship between biomarkers and gene carriers and NeuroCart scores, correlations and regression analyses will be used.

NeuroCart scores will be analysed with an analysis of variance (ANOVA) and/or multivariate analysis of variance (MANCOVA) to estimate differences between the groups of elderly with different Aβ status.

The intra- and inter-individual diurnal fluctuation will be investigated with mixed-model analysis.

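### Step 2 leaves penalisation optional without a criterion, and averaging the bootstrap coefficients does not make the predictions bootstrap-corrected

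*Protocol*

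**What the plan says.** Section 9.8.1 describes two steps; section 1.1.9 and the synopsis carry the same text.

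- **Step 1** fits LASSO logistic regression in 500 bootstrap samples, and the penalty is there "in order to account for the expected small event per variable ratio". Of the candidates, "the ones that consistently and most frequently appear in the bootstrap models will be selected". No frequency cut-off or number of variables is given.
- **Step 2** draws another 500 bootstrap samples. With the selected variables only, "logistic regression will be performed (with penalization if necessary) in each of the bootstrap samples". Then: "The estimates out of all the bootstrap models will be averaged and used in order to obtain predictions in the original data".
- **Label and assessment.** "Step two will result in the bootstrap-corrected predictions", and these are assessed by calibration slope, c-index and squared prediction error.

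On size, section 1.1.4 says "The aim for this study is to enroll 200 subjects" and "we expect to find at least 42 A β positive healthy elderly subjects".

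**The concern.** Step 2 produces the coefficients that are the study's product, and two things about it do not fit.

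First, the reason for penalising in step 1, few events per variable, applies equally to step 2, which uses the same events. Yet there the penalty becomes optional, with no criterion.

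Second, the text claims a correction that no described operation performs. It estimates no optimism, derives no shrinkage factor and uses no held-out or new subjects. Small-sample maximum-likelihood (ML) logistic coefficients lie too far from zero on average. A bootstrap sample treats the original fit as the truth and adds that bias again. The average of the bootstrap coefficients is therefore roughly the original fit plus one more helping of bias. A bootstrap bias correction would subtract that difference; the plan's average adds it.

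At stake are the calibration of the published algorithm and the credibility of the performance figures reported under that label.

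**Working it through.** **1. The plan's own figure.** Section 1.1.4 says "we can expect at least 19% amyloid pathology in a 65+ population and 23% amyloid pathology among cognitively healthy 70+ elderly subjects". With 100 subjects in each age group: 0.23 × 100 + 0.19 × 100 = 23 + 19 = 42 events in 200 subjects (21%). This reproduces the stated 42.

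**2. Events per variable.** Counting section 6.2 and the main objective in section 2, with each plasma marker once: tracking 1, VVLT 6, Milner Maze 9, face task 2, N-back 6, SART 6, tapping 2, EEG 15, saccades 3, smooth pursuit 1, CDR and IADL 2, grip 1, plasma 5, APOE 1, age and education 2. The sum is 62, so 42/62 = 0.68 events per candidate in step 1. In step 2 it is 42/k for k retained variables: 10.5 at k = 4, 4.2 at k = 10, 3.0 at k = 14. The protocol does not give k.

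**3. Step 2 alone, predictors fixed in advance.** Assumptions: n = 200, prevalence 21%, normal predictors with correlation 0.2, true c-index 0.70 to 0.78, 40 datasets per scenario, 500 bootstrap samples, 20,000 new subjects. Entries are medians, with ranges over the two c-index settings. Spread ratio = SD of the averaged linear predictor / SD of the single-fit linear predictor.

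| k | Spread ratio | New-data slope, single ML fit | New-data slope, averaged ML |
|---|---|---|---|
| 4 | 1.04-1.05 | 0.83-0.87 | 0.80-0.84 |
| 6 | 1.06-1.07 | 0.70-0.81 | 0.66-0.76 |
| 8 | 1.08-1.09 | 0.69-0.75 | 0.64-0.69 |
| 10 | 1.09-1.11 | 0.60-0.69 | 0.55-0.62 |
| 14 | 1.15-1.17 | 0.48-0.59 | 0.41-0.49 |

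The ratio exceeded 1 in every dataset. Averaging changed the c-index by at most 0.002. Averaging ridge fits instead, with the penalty from 10-fold cross-validation, gave slopes of 1.04 to 1.24.

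Two further simulations with the same n and about 42 events agree:

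- 6, 10 and 15 predictors: 6%, 11% and 18% wider; slopes 0.83/0.67/0.56 (single) and 0.77/0.61/0.47 (averaged).
- 4, 6, 10 and 15 predictors: 4%, 7%, 11% and 17% wider; slopes 0.88/0.77/0.65/0.53 (single) and 0.86/0.73/0.59/0.45 (averaged). Cross-validated ridge gave 1.01 to 1.09.

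**4. Both steps together.** 62 candidates, LASSO in 100 bootstrap samples, the 8 most frequent kept, averaging over 200 bootstrap samples, 724 datasets. Medians:

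- spread ratio 1.09;
- new-data slope 0.453 for the single ML fit, 0.415 for averaged ML, 0.628 for averaged ridge;
- averaged ML in the original data: slope 0.92, c-index 0.83; in new subjects: 0.42 and 0.69.

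Averaging accounts for (0.453 − 0.415)/(1 − 0.415) = 0.038/0.585, about 6% of the shortfall from a slope of 1. The rest comes from unpenalised fitting and from selecting on the same events.

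**5. Why assessment in the original data cannot show this.** A single ML fit has slope 1 in its own data by construction. If averaging multiplies the linear predictor by r, the slope there is about 1/r: 1/1.09 = 0.92, as found in item 4. That slope registers the widening from averaging and nothing of the overfitting.

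**6. What such slopes mean on the risk scale (illustration).** Assume predictions are right at the mean risk of 21% (logit −1.325), and take a predicted risk of 5% (logit −2.944). The 5% is an assumption, since the protocol fixes no cut-off. The difference is −1.619.

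- Slope 0.80: −1.325 − 0.80 × 1.619 = −2.620, a true risk of 6.8%.
- Slope 0.42: −1.325 − 0.42 × 1.619 = −2.005, a true risk of 11.9%.

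**The case against.** A reader might infer that step 2 is unpenalised as written. It is not: the same sentence allows a penalty, and with one the inflation disappears. A reader might also take the condition to mean separation or non-convergence. The documents do not say so. The only reason they give for penalising is few events per variable, and on that reading a penalty could well be applied when k is large. The rule may also stand in a SAP that is not at hand. All of this stands, so the point about penalisation is an open choice with no criterion, not a fixed error.

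It is also fair that averaging is the smaller cause, that ranking is practically untouched, and that the study is declared exploratory. With 4 pre-fixed predictors the loss is modest.

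Two things are not answered. Whatever the penalty, averaging coefficients and predicting in the original data estimates no optimism, so the label states a property the procedure lacks; a SAP that follows the protocol inherits it. And exploratory status does not turn apparent performance into corrected performance.

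**Conclusion.** The point holds in a conditional form. Step 2 leaves penalisation open although the protocol itself names the reason for it. If no penalty is used, averaging makes the predictions somewhat more extreme than one fit, on top of larger overfitting: a new-data slope of about 0.80-0.86 with 4 pre-fixed predictors and 0.41-0.49 with 14-15. With selection included and 8 of 62 variables kept, it is about 0.42. The bootstrap-corrected label is wrong in any case.

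The direction was the same in every scenario. The size rests on the assumed predictor correlation, true c-index and number of variables kept; the last is not stated, so it cannot be said that the algorithm will be badly calibrated.

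Nor do the documents support saying that lumbar punctures will be wrongly omitted. Section 1 mentions omission only as something that could be decided in future studies. Low predicted risks that are too low are a possible effect on that later use, no more.

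**What to change.** In 9.8.1, 1.1.9 and the synopsis:

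1. Remove the condition on the penalty in step 2 and penalise every fit by a prespecified rule, for example ridge with a cross-validated penalty. One penalised fit in the original data would serve as well as an average.
2. Drop the bootstrap-corrected label and call performance in the original data apparent, unless optimism is actually estimated. To estimate it, repeat both steps inside each outer bootstrap sample, take the performance in that sample minus the performance of the same model in the original data, and use the mean difference to correct the slope, c-index and squared error.

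**Cost.** Wording, standard methods and computing time: each outer sample needs 500 + 500 = 1,000 fits, so 200 outer samples (an assumed number) need 200,000. Coefficients are shrunk, so odds ratios are less directly interpretable, and they may be somewhat over-shrunk (slopes up to 1.24 with pre-fixed predictors). Step-2 penalisation alone does not remove selection optimism: the two-step slope rose from 0.42 to 0.63, not to 1. The second change is therefore needed for honest performance figures.

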If the ability of the algorithm to discriminate between subjects who are likely to have a biomarker profile indicative of AD pathology and subjects with a normal biomarker profile is confirmed by evidence of pathology in CSF, it could be decided to not perform lumbar punctures in subjects who are very likely to have a *normal* CSF biomarker profile based on the algorithm in future studies. This will allow for a noninvasive method to pre-select healthy subjects likely to have Aβ pathology in the

CSF and therefore to fewer healthy elderly subjects who will have to undergo a lumbar puncture. The results of this study can also be used for subject selection for research that specifically targets a certain biomarker (e.g NfL).

As an exploratory objective, plasma samples will be analyzed for diurnal fluctuation in this current study. Diurnal fluctuation in the concentration of CSF biomarkers has been reported and may represent a pre-analytical confounding factor in the laboratory diagnosis of AD [20]. Plasma biomarkers for AD have however not been extensively studied for possible fluctuating levels during the day. The results will also provide more information about the effect of the clearance systems of the brain which removes proteins (e.g. $A\beta$) from the brain via various overlapping clearance systems [21]. These clearance systems may be the cause of the diurnal fluctuation reported in CSF. This knowledge can be used in future clinical trials to perform certain assessments (e.g. LP and blood samples) at the most useful time points.

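### The algorithm's c-index, calibration slope and prediction error are in-sample figures, wrongly described as coming from bootstrap-corrected predictions

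*Protocol*

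**What the plan says.** Protocol 9.8.1 sets out a two-step procedure, repeated in 1.1.9 and in the synopsis under Statistical methodology.

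- Step 1: "In the first step 500 bootstrap samples will be generated out of the original data and logistic regression with LASSO penalization", with all candidates entered. The variables that recur most consistently and often are kept. No inclusion frequency, number of variables or penalty rule is given.
- Step 2: 500 new bootstrap samples are drawn and logistic regression is fitted, with a penalty if needed. "This time only the variables that were selected in step 1 will be entered in the model".
- Scoring: "The estimates out of all the bootstrap models will be averaged and used in order to obtain predictions in the original data".
- Label: "Step two will result in the bootstrap-corrected predictions". These are to be judged by calibration slope, c-index and squared prediction error.

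No hold-out sample, external sample or scoring of left-out subjects is named. Section 4.4 confirms the classification against CSF in the same subjects.

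On numbers, section 1.1.4 says "The aim for this study is to enroll 200 subjects" and "we can expect at least 19% amyloid pathology in a 65+ population and 23% amyloid pathology among cognitively healthy 70+ elderly subjects". It adds that "we expect to find at least 42" Aβ-positive subjects. Sections 9.3 and 9.8.2 call the study exploratory, with no formal hypothesis.

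**The concern.** A model scored on the subjects who chose and fitted it looks better than it will in new subjects. That optimism grows when many candidates compete for few events, as the protocol acknowledges here. A bootstrap can estimate and remove optimism, but only if each resample's model is compared between the resample and the original data, or scored on subjects left out, with selection repeated each time. The protocol does none of this.

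The figures bear on the main objective. The Background attaches a consequence to good performance, in a sentence that begins "If the ability of the algorithm to discriminate between subjects": if CSF confirms it, future studies might omit lumbar puncture in subjects predicted to be normal. A reader told that the predictions are corrected would take the c-index and slope as estimates for new subjects.

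**Working it through.** **The plan's own figure.** Section 1.1.4: 100 × 0.23 + 100 × 0.19 = 23 + 19 = 42 positives. This reproduces the stated 42, and 42/200 = 21%.

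**Candidates (assumed count).** Section 6.2, without the screening-only MMSE and GDS: tracking 1, VVLT 6, maze 9, faces 2, N-back 6, SART 6, tapping 2, EEG 15, saccades 3, smooth pursuit 1, CDR 1, IADL 1, grip 1 = 54. Adding 5 plasma markers, APOE, age and education gives 62, or 64 with MMSE and GDS. Events per candidate: 42/62 = 0.68.

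**What is scored.** Let D be the 200 subjects, S(D) the step-1 selection and β̄ = (1/500) Σ β̂(D*ᵦ, S(D)) the averaged coefficients. The plan reports performance(β̄; D). Optimism is performance(β̄; D) minus performance(β̄; new subjects), and no step estimates it. A subject is missing from one bootstrap sample with probability (1 − 1/200)^200 ≈ 0.37. Each subject's outcome therefore enters about 500 × 0.63 ≈ 316 of the averaged fits, as well as S(D). The averaged model is not independent of anyone it scores.

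**Size with no signal.** Simulated: 200 subjects, 42 positives assigned at random, 62 independent candidates, 500 + 500 bootstraps, unpenalised step 2. The selection rules are assumed, because the protocol gives none. The true c is 0.50 and the true slope 0; the same models in new subjects gave c 0.50 and slope 0.00 to 0.01. The bracketed range, slope and share of data sets belong to the penalty tuned by cross-validation within each bootstrap (60 data sets). The last column uses one penalty tuned once on the original data (100 data sets).

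| Rule | Mean no. kept | Reported c (95% range) | Slope | Data sets with c ≥ 0.70 | c, single tuned penalty |
|---|---|---|---|---|---|
| Top 3 | 3 | 0.68 (0.63–0.74) | 0.97 | 28% | 0.69 |
| Top 5 | 5 | 0.72 (0.68–0.78) | 0.95 | 77% | 0.72 |
| Top 10 | 10 | 0.78 (0.73–0.84) | 0.91 | 100% | 0.77 |
| ≥50% | 12.1 | 0.79 (0.61–0.90) | 0.89 | 90% | 0.56 |
| ≥70% | 3.6 | 0.67 (0.50–0.84) | 0.96 | 47% | 0.54 |
| ≥80% | 1.6 | 0.61 (0.50–0.79) | 0.97 | 25% | 0.53 |
| ≥90% | 0.4 | 0.54 (0.50–0.75) | 0.96 | 10% | 0.52 |

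The Brier score for the top 10 was 0.135 in the original data and 0.202 in new subjects. Correlated predictors (0.5) changed little. A separate simulation with one fixed penalty gave 0.73 (top 5), 0.78 (top 10), 0.71 (≥50%) and 0.55 (≥80%).

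**Size with signal (effect sizes assumed).**
- Modest signal in three variables, top 5, 40 data sets: reported c 0.77 and slope 0.95, against 0.60 and 0.31 in new subjects.
- Log-odds 1.0/0.8/0.5 or 1.5/1.0/0.6 per SD, ≥80% rule: reported c 0.77–0.85 against a true 0.73–0.84, a gap of 0.01–0.04. With top 5 kept: 0.85 against 0.75, and 0.89 against 0.82.

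**Which repair works (no signal).**
- Optimism correction of step 2 only, selection held fixed: c stays at 0.68–0.69 (top 5) and 0.71–0.72 (top 10).
- Whole procedure repeated in an outer optimism bootstrap (top 5, 12 data sets, 40 outer resamples): c 0.58, slope 0.42.
- Whole procedure repeated in each fold of 10-fold cross-validation (same 12 data sets): c 0.48. A separate run gave 0.47.

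**The case against.** The strongest reply is that the damage depends on choices the protocol has not made. It asks for variables that recur consistently as well as frequently, and a forced top 5 or top 10 ignores the first word. Under strict inclusion rules, or threshold rules with one penalty tuned on the full data, the null c is mostly 0.5 to 0.6, often because nothing is selected. With strong predictors and strict selection the gap nearly vanishes. A complete null is also a hard test, since the protocol links APOE and age to amyloid. This stands, and it limits the size. A reader might infer that the plan would look convincing even with no signal whatever rule is used; the text does not support that.

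A reader might also infer that the calibration slope must look near-ideal, or that averaging always inflates coefficients. Step 2 allows a penalty, and with ridge in a null top-5 run the in-sample slope was about 1.75. The c-index stayed at 0.73, so that option does not cure the optimism.

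The label is attached to the predictions rather than to the c-index by name. But the measures are computed from those predictions, so the description carries over.

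The study is exploratory, no decision within it turns on the c-index, and omitting punctures is only a possibility for later studies. That lowers the consequence. It does not make an in-sample figure a corrected one. An SAP could add validation, but the protocol already fixes this procedure and names its result in three places.

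**Conclusion.** Wrong as written. The c-index, calibration slope and squared prediction error for the main objective are apparent performance, described as coming from bootstrap-corrected predictions. This follows from the text and needs no simulation.

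The size is conditional. With no signal the reported c is about 0.68 to 0.79, with an unpenalised slope of about 0.9 to 0.97, if the top 3 to 10 variables are kept or if at least 50% inclusion is combined with a penalty tuned within each bootstrap. It is about 0.5 to 0.6 under inclusion cuts of 80 to 90%, or under threshold rules with a single penalty tuned on the original data. With a modest signal and top 5 it is about 0.77 against 0.60. With strong signals and strict selection the gap is small. These figures rest on 62 to 64 candidates, 42 positives, and assumed selection rules, penalty tuning and effect sizes.

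**What to change.** In 9.8.1, 1.1.9 and the synopsis:

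- Repeat the whole procedure inside each fold of repeated cross-validation: any transformation, penalty tuning, step-1 selection with a pre-set inclusion-frequency cut, and the step-2 fit.
- Report the c-index, calibration slope and squared prediction error from the held-out subjects as the main performance result. A full-loop optimism bootstrap may be shown alongside, with a note that some optimism remains.
- Add no imputation to the loop, since section 9.4 says missing test results are not imputed.
- Remove the term bootstrap-corrected from the current step 2, and report its figures only as apparent performance.
- Describe the whole as internal validation only.

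The cost is wording in three places, programming and computing time. Reported performance will be less favourable. No new data are needed.

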2 STUDY OBJECTIVES

Main objectives:

To define an algorithm based on the plasma biomarkers: A β 40, A β 42, t-Tau, p-Tau, NfL and APOE ϵ status and NeuroCart tests, age, grip strength and level of education that distinguishes between positive and negative A β CSF in healthy elderly.

Exploratory objective:

To determine the correlation between AD-specific biomarkers in CSF (Aβ 1-40 and 1-42, Tau proteins, NfL) and the NeuroCart scores in a cohort of 200 healthy elderly subjects.

To determine the correlation between AD-specific biomarkers in plasma (Aβ 1-40 and 1-42, Tau proteins, NfL) the NeuroCart scores in a cohort of 200 healthy elderly subjects.

To determine the correlation between AD-specific biomarkers in CSF (Aβ 1-40 and 1-42, Tau proteins, NfL) and in plasma in a cohort of 200 healthy elderly subjects.

To determine the correlation between APOE ϵ genotype and the A β /Tau/NfL concentrations in CSF in a cohort of 200 healthy elderly subjects.

To determine the correlation between APOE ϵ genotype and the A β /Tau/NfL concentrations in plasma in a cohort of 200 healthy elderly subjects.

To characterize the cohort of healthy elderly subjects in order to yield norm scores for specific NeuroCart tests in all subjects.

To characterize the plasma biomarkers across multiple times of day to gain understanding of intraand inter-subject variability, and thus diurnal fluctuation.

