o Handgrip strength dominant hand

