As handgrip strength may serve as a predictor of cognitive loss with advancing age [55], the JAMAR dynamometry is used in this study. The subject sits comfortably in a standard chair with legs, back support and fixed arms. The subject will be asked to rest the forearms on the arms of the chair with the wrist just over the end of the arm of the chair—wrist in a neutral position, thumb facing upwards. The subject must be demonstrated how to use the Jamar handgrip dynamometer to show that gripping very tightly registers the best score. The subject should perform this test with the dominant hand. The subject should position the hand so that the thumb is round one side of the handle and the four fingers are around the other side. The instrument should feel comfortable in the hand of the subject. The position of the handle can be altered if necessary. The observer should rest the base of the dynamometer on the palm of the hand of the subject as the subject holds the dynamometer. The aim of this is to support the weight of the dynamometer (to negate the effect of gravity on peak strength), but care should be taken that its movement is not restricted. The subject must be encouraged to squeeze as long and as tightly as possible. The measurement outcome (grip strength in kilograms) is digitally recorded in the data collection form and will be repeated twice to give three readings in total. The best of the three grip strength measurements is used in statistical analyses so as to encourage the subjects to get as high a score as possible. The hand dominance, i.e. right, left or ambidextrous (people who can genuinely write with both hands) of the subject must be recorded. This method is adapted from the standardised method of Roberts et al [56].

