9.7 Baseline parameters and concomitant medications

9.7.1 Demographics and baseline variables

Continuous demographic variables (e.g., age, height, weight, BMI) will be summarized by descriptive statistics (n, mean, SD, median, Min, Max).

Qualitative demographic characteristics (sex, race/ethnicity) will be summarized by counts and percentages.

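### Sex is left out of the fixed list of candidate predictors although raw grip strength in kilograms is on it, and the ANOVA/MANCOVA wording leaves open whether NeuroCart comparisons are adjusted

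*Protocol*

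**What the plan says.** **Candidate predictors.** The main objective in Protocol section 2 names plasma markers, APOE status and "NeuroCart tests, age, grip strength and level of education". Section 9.8.1 enters "all the candidate variables (CNS and biochemical outcome variables, age and educational level" into the LASSO step. The synopsis and sections 1 and 1.1.9 repeat these lists. Sex is in none of them.

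**Grip strength.** Section 6.2 lists "Handgrip strength dominant hand" among the CNS outcome variables, so grip is a candidate under section 9.8.1 as well as under the objective. Section 7.3 states: "The measurement outcome (grip strength in kilograms) is digitally recorded in the data collection form". The highest of three readings is analysed. No sex-standardised score is described.

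**Sex.** Section 4.2 admits men and women aged 65 and over. The only stated analytic use of sex is in section 9.7.1: "Qualitative demographic characteristics (sex, race/ethnicity) will be summarized by counts and percentages".

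**NeuroCart by amyloid status.** Section 9.8.1 (repeated in the synopsis and section 1.1.9) states: "NeuroCart scores will be analysed with an analysis of variance (ANOVA) and/or multivariate analysis of variance (MANCOVA". No covariate is named.

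**Associations.** The same section states: "To investigate the relationship between biomarkers and gene carriers and NeuroCart scores, correlations and regression analyses will be used". Again no covariate is named.

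**The concern.** Two separate matters are at stake.

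The first bears on the main objective. Grip strength in kilograms usually differs between men and women. If sex is not a candidate, the model cannot separate a weak grip for a man from an ordinary grip for a woman. A real within-sex signal is then blurred, and a chance difference in sex mix between the amyloid groups shows up as a grip difference.

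The second bears on exploratory analyses. The protocol says amyloid pathology increases with age, sets no upper age limit, and requires at least 100 subjects over 70 so that age can be differentiated. Section 7.3 reports lower sustained-attention performance in healthy elderly than in healthy young subjects. The group comparison and the correlations nevertheless name no age term. The method label also contradicts itself: it expands as multivariate analysis of variance but carries the acronym of multivariate analysis of covariance. The abbreviation list defines ANCOVA, but the methods text never uses it.

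**Working it through.** **1. The plan's own figure.** Section 1.1.4 expects 23% of 100 subjects over 70 and 19% of 100 subjects aged 65-70 to be amyloid positive: 100 × 0.23 + 100 × 0.19 = 42 positive and 158 negative of 200. This reproduces the stated figure of at least 42. For a comparison of 42 with 158 in SD units, SE = √(1/42 + 1/158) = 0.174. The difference detectable with 80% power is (1.96 + 0.84) × 0.174 = 0.49 SD (two-sided 5%, assumed, since the protocol sets no test level).

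**2. Raw grip without sex.** Let D be the male-female difference in within-sex SDs. The protocol gives no value, so 1.0 to 2.5 is assumed, with a 50:50 sex mix and sex unrelated to amyloid status. The SD of the pooled cohort is √(1 + D²/4) within-sex SDs, so a within-sex effect shrinks by the factor 1/√(1 + D²/4). For an assumed within-sex effect of 0.5 SD, single-predictor power is Φ(effect/0.174 − 1.96):

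| D | Factor | Loss | Effective size | Power |
|---|---|---|---|---|
| sex accounted for | 1 | 0 | 0.50 | 82% |
| 1.0 | 0.894 | 10.6% | 0.45 | 73% |
| 1.5 | 0.800 | 20.0% | 0.40 | 63% |
| 2.0 | 0.707 | 29.3% | 0.35 | 53% |
| 2.5 | 0.625 | 37.5% | 0.31 | 44% |

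The chance SE of the difference in sex share between the amyloid groups is 0.5 × 0.174 = 8.7 percentage points. A 10-point imbalance is therefore unremarkable. It would produce a grip difference of 0.10 × D = 0.10 to 0.25 within-sex SD unrelated to amyloid.

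**3. Age bias in the unadjusted amyloid-group comparison.** On the protocol's counts the shares over 70 are 23/42 = 54.8% of positives and 77/158 = 48.7% of negatives, a gap of 6.0 points. Bias = 0.060 × the score difference between the two age bands. For assumed differences of 0.25, 0.5 and 1.0 SD, the bias is 0.015, 0.030 and 0.060 SD, and a nominal 5% test runs at 5.1%, 5.3% and 6.4%.

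The 19% is given for the whole 65+ population but applied to ages 65-70. If the younger band's prevalence were 10% to 15% (assumed), positives would number 33 to 38 and the age gap would be 24 to 13 points. With a 0.5 SD age-band difference, the bias would be about 0.12 to 0.06 SD. This uses two age bands only and ignores age variation within them.

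**4. Precision.** If age, sex and education explain an assumed 20% to 30% of score variance, adjustment is worth 1/(1 − R²) = 1/0.8 to 1/0.7, that is, 25% to 43% more subjects.

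**5. Crude biomarker-NeuroCart correlations.** If age is the only link, the crude correlation equals r(age, marker) × r(age, score). The chance of p < 0.05 at n = 200 follows from Fisher's z with √197. All inputs are assumed:
- 0.5 and −0.4: r = −0.20, z = 2.85, significant in 81% of studies.
- 0.4 and −0.3: r = −0.12, z = 1.69, about 39%.
- 0.3 and −0.3: r = −0.09, z = 1.27, about 24%.

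**The case against.** A reader might infer that the protocol plans these analyses without adjustment. It does not say so. Regression is named for the associations and the MANCOVA acronym for the group comparison, and both can carry covariates. A covariate list for exploratory analyses is commonly left to the SAP, which is not at hand, so its absence alone is no finding. What stands against the protocol is narrower: the method label is inconsistent, and plain ANOVA meets it.

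A reader might also infer that age seriously biases the amyloid-group comparison. On the protocol's own counts it does not: the bias is at most 0.06 SD over the assumed range, against a detectable 0.49 SD. Nor does a missing age or education term reach the main objective, since both are already candidates in the algorithm.

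On sex, it is tempting to call grip largely a stand-in for sex. The protocol gives neither a male-female grip difference nor a link between sex and amyloid status, so this cannot be established. The aim is prediction, LASSO tends to drop an uninformative proxy, and grip is one of many candidates. The likely harm is dilution of that one predictor. The omission itself still stands, because the protocol fixes the list rather than leaving it to the SAP.

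Finally, crude CSF-plasma correlations bear directly on whether plasma can screen for CSF status. Replacing them with partial correlations would answer a different question and is not needed.

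**Conclusion.** The point holds in two parts.

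- **Candidate list.** Sex is missing while unstandardised grip is included in a mixed-sex cohort. This concerns the main objective but is limited to one predictor: a 10.6% to 37.5% loss of a within-sex effect, resting on the assumed sex difference, an equal sex mix and no sex-amyloid link.
- **Method label.** The ANOVA/MANCOVA wording contradicts itself and leaves adjustment undefined. For the amyloid-group comparison the benefit of adjusting is mainly precision. For biomarker-NeuroCart correlations, shared ageing could produce apparent associations.

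The rates of 24% to 81% and the 25% to 43% gain illustrate assumed correlations and explained variance; they are not predictions for this cohort. Sections 2 and 7.3 make these comparisons exploratory, and section 9.8.2 sets no formal null hypothesis. The protocol's main conclusion is not overturned; this is an inexpensive improvement worth making.

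**What to change.** 1. Add sex to the candidate predictors in sections 2 and 9.8.1 and in their repeats in the synopsis and sections 1 and 1.1.9. Alternatively, enter grip strength standardised by sex.
2. Replace the ANOVA/MANCOVA sentence with a comparison of NeuroCart scores by amyloid status adjusted for age (continuous), sex and education: ANCOVA per endpoint, or MANCOVA, correctly expanded, where a joint test is wanted.
3. For biomarker-NeuroCart associations, report regression or partial correlations adjusted for the same three variables beside the crude values. CSF-plasma correlations may stay crude.

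**Cost.** No new procedure is needed: age and sex are summarised as baseline data and education is already a planned candidate. The changes use a few degrees of freedom out of 200 and add one LASSO candidate. Because the list is part of the main objective, adding sex may require an amendment under section 10.6.2. Per-endpoint ANCOVA also means many univariate tests without multiplicity adjustment (section 9.8.2), so those results should be read as exploratory.
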